### 10.3.1.3 Joint Replacement Questionnaire

The investigator will judge the likelihood of the need for joint replacement surgery, based on KOOS subscales and subject satisfaction outcomes.

The subject will judge the likelihood of the desire for joint replacement surgery, based on their personal response to treatment with CNTX-4975-05.

### 10.3.1.4 Subject Satisfaction Questionnaire

Subjects will be asked to rate their overall satisfaction with the treatment procedure. Subjects with a PJR/TJR will also compare their satisfaction with their PJR/TJR versus their CNTX-4975-05 treatment. These will be rated using the following 7-point scale:

- 1 Completely dissatisfied
- 2 Mostly dissatisfied
- 3 Somewhat dissatisfied
- 4 Neither satisfied or dissatisfied
- 5 Somewhat satisfied
- 6 Mostly satisfied
- 7 Completely satisfied

Subjects will also be asked whether they would undergo the study treatment again.

#### 10.3.1.5 Investigator Satisfaction Questionnaire

The investigator will rate his or her satisfaction with the subject's study treatment.

The investigator will rate his or her satisfaction with the treatment procedure.

#### 10.3.1.6 Rescue Medication Use

Subjects may take rescue medication for pain of the index knee as described in Section 9.12.1, except that they should not use rescue medication within 24 hours before a planned study visit. Data on the type of rescue medication and background analgesics for knee OA, and the daily dose, will be reported daily by the subject on a paper diary from Screening through Week 8/ET. Additional rescue medication details will be collected at study visits and follow-up telephone calls in the source documents and in the eCRF.

### 10.3.2 Clinical Pharmacology

Not applicable for this study.

### **10.3.3** Safety

Safety will be assessed by injection site assessments (erythema and edema), assessment of procedure pain, AEs, physical examination findings, vital sign measurements, 12-lead ECG findings, clinical laboratory test results, and sensory testing.

### 10.3.3.1 Laboratory Safety Assessments

### 10.3.3.1.1 Laboratory Tests to be Performed

Samples for the following laboratory tests will be collected at the time points specified in the schedule of events (Section 2).

Hematology hemoglobin, hematocrit, red blood cell count, red blood cell indices,

mean corpuscular hemoglobin, mean corpuscular hemoglobin concentration, platelet count (or estimate), white blood cell count

including differential

Serum Chemistry albumin, total bilirubin, total protein, calcium, alkaline phosphatase,

alanine aminotransferase, aspartate aminotransferase, blood urea nitrogen, creatinine, glucose, sodium, potassium, chloride,

bicarbonate, lactate dehydrogenase, uric acid

Coagulation Panel prothrombin time, partial thromboplastin time, fibrinogen

Urinalysis pH, specific gravity, occult blood, leukocyte esterase, glucose, protein,

ketones

Urine Pregnancy Test Only for women of childbearing potential. A serum pregnancy test will

be performed if the urine pregnancy test is positive.

Urine Drug Screen amphetamines, barbiturates, benzodiazepines, cocaine, opiates,

phencyclidine, and tetrahydrocannabinol

Other HgbA1c

Knee Radiographs Radiographs of both knees using standard standing films or using the

fixed flexion method. Scoring will use the Kellgren-Lawrence Grading

Scale.

Blood and urine samples for hematology, serum chemistry, and urinalysis will be sent to a central laboratory for analyses. Urine drug screens and urine pregnancy tests may be conducted at the study sites.

#### 10.3.3.1.2 Specimen Handling Requirements

The transmission of infectious agents may occur through contact with contaminated needles and blood or blood products. Consequently, appropriate blood and body fluid precautions should be employed by all study personnel involved in the collection of blood and handling of specimens in

both the clinic and laboratory settings. Refer to current recommendations of the appropriate authorities.

### 10.3.3.1.3 Evaluation of Laboratory Values

The normal ranges of values for the laboratory assessments in this study will be provided by the responsible laboratory and submitted to Centrexion Therapeutics Corp. prior to the beginning of the study. They will be regarded as the reference ranges on which decisions will be made.

If a laboratory value is out of the reference range, it is not necessarily clinically relevant. The investigator must evaluate the out-of-range values and record his or her assessment of the clinical relevance in the appropriate eCRF.

All laboratory values that, in the investigator's opinion, show clinically relevant or pathological changes during or after termination of the treatment have to be reported as AEs and followed as described in Section 11.2.6.

All measurements described in this section are recognized standard methods.

#### 10.3.3.2 Clinical Examinations

#### **10.3.3.2.1 Vital Signs**

Vital signs measurements will be conducted according to the schedule of events, Section 2 and will include systolic and diastolic blood pressure, heart rate (HR) and respiratory rate (RR), and will be measured with the subject standing and also after the subject has been in a sitting position for 5 minutes. Temperature will also be measured at all office visits.

#### 10.3.3.2.2 Electrocardiogram

A standard 12-lead ECG will be performed at rest, with the subject lying down for approximately 5 minutes before the ECG is obtained. The ECG will be evaluated at the investigational site to determine the subject's eligibility and to monitor safety during the trial. The principal investigator or qualified designee will review, sign, and date each ECG reading, noting whether or not any abnormal results are of clinical significance. The ECG will be repeated if any results are considered to be clinically significant. All ECG recordings will be identified with the subject number, initials, date, and time of the recording.

### 10.3.3.2.3 Physical Examination

Complete (excluding a genitourinary exam) or partial physical examinations will be conducted according to the schedule of events, Section 2. The investigator should assess periarticular tenderness and pain in the soft tissue of the injected knee(s) at each physical examination and record the results on the eCRF. At each physical examination, the investigator should also listen to the heart and lungs at a minimum and follow up any symptoms with a targeted physical exam, as appropriate.

Height and weight will be measured at the Screening Visit. Knee circumference will be measured at Screening.

The principal investigator or his or her appointed designee is primarily responsible for performing the physical examination. Whenever possible, the same individual should perform all physical examinations if feasible.

#### **10.3.3.2.4 Injection Site Assessment**

The injection site will be examined and assessed for erythema and edema (separately by an investigator using a categorical scale of none, mild, moderate, or severe) before each CNTX-4975-05 injection, after each injection at 1 and 2 hours post-dose, and at the Week 4 study visit. Significant bruising or other clinically significant injection site reactions (other than erythema or edema) will be recorded as AEs.

#### 10.3.3.2.5 Sensory Testing

Sensory testing will be performed before each CNTX-4975-05 injection and at Week 8/ET. The following sensory tests will be performed bilaterally:

- Position sense at the knee and great toe
- Vibratory sense at the patella (measured via 128 Hz tuning fork)
- Light touch assessed over the patella, the popliteal area, and the top of the foot
- Pinprick sensibility tested at the top of the foot and over the patella

Each of the above sensory tests will be graded using the following 5-point Likert Scale:

Finding	Score	Definition	
Normal	4	Normal sensory function, sensory response as expected in a normal subject	
Mild Deficit	3	Defined as a possible, inconsistent deficit	
Moderate Deficit	2	Defined as a clear, consistent deficit	
Severe Deficit	1	Defined as a major impairment	
Absent Sensation	nt Sensation 0 Defined as a complete loss of sensation		

The use of the 5-point Likert Scale (0-4) will be based on the clinician's assessment.

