- f. Medical history and demographics, as outlined in the eCRFs. OA medications should note all therapies, including doses and regimen when known, and all should note if the medications were over the counter or prescriptions. Treatments to be recorded include non-invasive treatments (e.g., physical therapy) and previous invasive treatments (e.g., arthrotomy, arthroscopy with procedure, if known).
- g. A complete physical examination (excluding a genitourinary examination) will be performed by the investigator at the Screening Visit and at the final clinic visit (Week 8/ET). A partial physical examination will be performed by the investigator before each injection). The physical examinations will also evaluate the soft tissue of the index knee for periarticular painful sites, which will be entered onto the case report form.
- h. To be performed before injection of CNTX-4975-05.
- i. Clinical laboratory tests will include chemistry, hematology, and urinalysis. Additional tests, including fibrinogen and prothrombin time/partial thromboplastin time, will be done at Screening only. Hemoglobin A1c will be done at the Screening and Week 8/ET Visits. Subjects are to fast prior to the laboratory sample collections performed at the Screening Visit. If the subject is receiving a second knee injection (in the contralateral knee), labs are not required to be repeated if the injection is within 30 days of the screening lab draw (at the investigator's discretion).
- j. Urine drug screen must be confirmed as negative for drugs of abuse prior to treatment. For subjects being treated bilaterally, a Urine Drug Screen is not required prior to the second injection.
- k. Subjects will be tested for pregnancy if they are women of childbearing potential. A serum pregnancy test will be performed if the urine pregnancy test is positive. Subjects with positive urine pregnancy test results will not be enrolled or will be discontinued from study participation. These subjects will be followed until the pregnancy is completed, and the health of the infant is known.
- 1. Vital signs are to be performed standing and sitting within approximately 5 minutes before the injection of IP, and sitting-only vital signs within approximately 5, 15, and 30 minutes minutes after the injection of IP.
- m. Each site is to follow their assigned, protocol-specified treatment regimen and the protocol-specified CNTX-4975-05 administration procedures.

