# 5.2 Summary of Potential Risks and Benefits

The potential benefits of study participation are that subjects with painful OA of the knee 1) may experience a reduction in acute and chronic, moderate-to-severe pain as a result of treatment with CNTX-4975-05, and 2) will understand that they are contributing to the scientific knowledge that may lead to expansion of the treatment options for subjects with OA. No other benefits of participation are anticipated.

The potential risks of study participation include those associated with exposure to CNTX-4975-05 and the risks of medical evaluation, including venipuncture and IA injection. Subjects will be injected with 1% or 2% lidocaine (without epinephrine) to provide distension of the joint capsule for access to the whole joint for CNTX-4975-05 and secondarily for sensory blockade. In principle, subjects with substantial reduction of pain and improvement in function after injection could overuse the joint and subject the index joint to overuse and an acceleration of the knee OA.

A summary of the pharmaceutical properties and known potential risks of CNTX-4975 is provided in the current version of the investigator's brochure (IB). The investigator must become familiar with all sections of the CNTX-4975-05 IB before the start of the study.

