#### 9.3.1 Pre-Medication

Prior to the injection procedure, the investigator may, at his or her discretion, pre-medicate subjects with an oral dose of an opioid or NSAID. The skin at the point of the anticipated injection(s) may also be infiltrated with 1 to 2 mL of lidocaine and/or a topical analgesic such as ethyl chloride spray. It is recommended not to use more than 2 methods of local analgesia about the knee(s) to be injected.

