#### 10.1 Study Visits

### 10.1.1 Screening Visit, Day -14 to Day 1, Visit 1

The subject must be screened within 14 days before enrollment into the study. The following procedures will be performed at screening.

- Written informed consent
- Confirmation of knee OA K-L grade (1 to 4) of the knee, based on radiographs
- Confirmation of diagnosis of knee OA, based on ACR diagnostic criteria
- Inclusion/exclusion criteria
- Height and weight (BMI)
- History of cancer
- Knee pain with walking (during last 24 hours, assessed in the clinic using NPRS of 0-10)
- Demographics
- Medical history, including current OA medications (prescription and non-prescription medications) and treatment history (including noninvasive or previous invasive treatments)
- HADS
- FSS
- Knee circumference
- Complete physical examination
- ECG
- Clinical laboratory testing (fasting)
- Urine drug screen
- Urine pregnancy test
- Vital signs
- Issue paper diary to the subject with instructions on use and recording of background analgesic and rescue medication for index knee (or bilateral knee for subjects being treated for both knees)

### 10.1.2 Treatment, Day 1, Visit 2

As 2 cases of severe allergic reactions have occurred in the entire CNTX-4975 program, a crash cart and personnel certified in advanced cardiac life support (ACLS) should be immediately available. See section 11.2.1 for details.

The following procedures will be performed on Day 1.

- Knee pain with walking (during last 24 hours, assessed in the clinic using NPRS of 0-10)
- Partial physical examination
- ECG
- Urine drug screen
- Urine pregnancy test
- Vital signs (before and after injection of CNTX-4975-05). All subjects must be monitored for at least 30 minutes (or longer, as required by the protocol) after study drug injection to ensure that they do not have a hypersensitivity reaction/anaphylaxis. Vital signs (VS) are to be done standing and sitting within approximately 5 minutes before the injection of IP, and sitting-only vital signs within approximately 5, 15, and 30 minutes after the injection of IP.
- Injection site assessment (erythema, edema) before injection and 1 and 2 hours after the injection
- Review paper diary
- Sensory testing
- Subject assessment of procedure pain (using 0-4 scale)
  - o at rest prior to pre-medication;
  - o prior to IA lidocaine (without epinephrine);
  - o at rest 10 minutes (±2 minutes) after IA lidocaine (without epinephrine);

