# 13.4.4.7 Sensory Testing

The number and percentage of subjects with each sensory assessment categorized from normal to absent, using a 5-point Likert Scale, where 0=absent sensation and 4=normal sensation, will be summarized at each time point.

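### The pre-injection sensory test may fall after cooling or local anesthesia, and its summary shows neither shift from baseline nor injected limb, so new deficits cannot be reliably identified or attributed

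*Combined protocol and SAP*

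**What the plan says.** Sensory testing is a listed safety endpoint (Section 13.1.4). Section 10.3.3.2.5 sets its timing: "Sensory testing will be performed before each CNTX-4975-05 injection and at Week 8/ET". The Schedule of Events marks it at Visits 2, 4 and 7 only. At Visits 2 and 4 it carries footnote h, which reads "To be performed before injection of CNTX-4975-05". The visit lists in Sections 10.1.2 and 10.1.4 name the test without a time. They are not chronological, because injection-site checks due 1 and 2 hours after injection stand above it.

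All five regimens in Section 9.3.2 cool the knee and give 15 mL of intra-articular lidocaine before CNTX-4975-05. Under Section 9.3.1 the skin "may also be infiltrated with 1 to 2 mL of lidocaine and/or a topical analgesic such as ethyl chloride spray". Section 5.2 describes the intra-articular lidocaine as given for joint distension "and secondarily for sensory blockade".

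Procedure pain, by contrast, is anchored to these steps: its first rating in Section 10.1.2 is "at rest prior to pre-medication" and its second precedes lidocaine.

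On sides and sites, Section 10.3.3.2.5 says "The following sensory tests will be performed bilaterally", and the light-touch item reads "Light touch assessed over the patella, the popliteal area, and the top of the foot". The analysis in Section 13.4.4.7 is the number and percentage of subjects in each category of a 5-point scale, "where 0=absent sensation and 4=normal sensation, will be summarized at each time point". Laboratory values, in Section 13.4.4.2, get shift tables.

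**The concern.** Section 5.1.1 says that capsaicin desensitizes nociceptors for weeks, with degeneration and later regrowth of their terminals. A lasting sensory deficit is therefore a question that the drug's mechanism raises, and this is the assessment that addresses it. Every subject receives CNTX-4975-05 (Section 9.5), so there is no placebo group. Inference about the drug must come from change within a limb and from comparing the injected limb with the uninjected one.

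The text weakens both. A baseline on a cooled or anesthetized knee may record a deficit that the subject does not have in ordinary conditions, and the possible exposure differs by regimen. A table of percentages per visit then nets resolved deficits against new ones. Because both limbs are tested but subjects are counted, it is also undefined which limb a subject's category refers to.

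**Working it through.** The documents state no event rate, sample size or power for sensory testing, so there is no figure to reproduce. The check compares the text on timing and then illustrates size under stated assumptions.

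**1. Time before CNTX-4975-05 in which a compliant test could fall** (Section 9.3.2). Start of cooling to drug = pre-lidocaine cooling + interval from lidocaine to drug.

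| Group | Pre-lidocaine cooling (min) | Lidocaine to drug (min) | Start of cooling to drug, at least (min) |
|---|---|---|---|
| 1 | 15 | 30 | 45 |
| 2 | 40 | 10 | 50 |
| 3 | 30 | 5 | 35 |
| 4 | 45 | 3 | 48 |
| 5 | 45 | 3 | 48 |

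These are the longest preparation times that could precede a compliant test. They are not usable testing time, since the wrap or gel pack is on for most of them.

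**2. Tests exposed** (Section 10.3.3.2.5). Per limb: position 2, vibration 1, light touch 3, pinprick 2, so 2 + 1 + 3 + 2 = 8. At the knee: 1 + 1 + 2 + 1 = 5. The other 3 are at the foot or great toe, away from the cooled area.

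**3. What a percentage-per-visit table shows.** Let *b* be the true deficit rate before the procedure, *c* the extra rate at baseline caused by cooling or anesthesia, and *d* the true new deficit rate at Week 8. Baseline = *b* + *c*; Week 8 = *b* + *d*; apparent change = *d* − *c*. All three are assumptions. With *b* = 10% and *d* = 10 points:

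| *c* (points) | Baseline | Week 8 | Apparent change |
|---|---|---|---|
| 0 | 10% | 20% | +10 |
| 5 | 15% | 20% | +5 |
| 10 | 20% | 20% | 0 |
| 20 | 30% | 20% | −10 |

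With *d* = 5 points the apparent change is +5, 0, −5 and −15. The Week 8 column does not depend on *c*: the deficits stay visible and only the change is distorted. The same subtraction applies if *c* is a group of genuine baseline deficits that resolve by Week 8.

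A shift table separates new from resolved deficits. It cannot repair a numbed baseline: a limb dulled by one category at baseline and truly down one category at Week 8 shows no shift. The timing and the table therefore each need correction.

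**4. Dilution if all tested knees were pooled.** With about 850 subjects (Section 13.2) and at least 150 of each type (Section 9.5), bilaterally injected subjects number from 150 to 850 − 300 = 550. Injected share of tested knees = (850 + bilateral) / 1,700, from 1,000/1,700 = 58.8% to 1,400/1,700 = 82.4%. An assumed 5% new-deficit rate in injected knees, with none elsewhere, would show as 5% × 0.588 = 2.9% to 5% × 0.824 = 4.1%. This assumes that the type targets are met and all second injections given.

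**5. Visit 4.** Visit 4 is Day 7 with a window of −2 to +5 days, so Day 5 to Day 12 under the standard window. The test then is a baseline for the contralateral knee but an early post-injection result for the index knee. A table by time point alone does not distinguish them.

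**The case against.** The strongest reply is that the protocol means testing before the whole procedure. Section 10.1.2 lists the injection procedure, with lidocaine and cooling, as one item. Footnote h also covers the physical examination, ECG and urine tests, a routine pre-procedure work-up. Many sites may well test first. But the text does not say so, and elsewhere the protocol uses injection for the drug alone: vital signs fall within about 5 minutes before the product is injected, which in Groups 1 and 2 is after lidocaine. Optional skin anesthesia also precedes the procedure on either reading.

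Second, a post-lidocaine test is hardly practicable in Groups 4 and 5, where the drug follows through the same needle after 3 minutes. In Groups 1 to 3 it would interrupt cooling or come just before an aseptic injection. This stands. A test on a cooled knee, for example when the wrap comes off for lidocaine, remains possible in every group.

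Third, a reader might infer that capsaicin-induced sensory loss would go undetected. The documents do not support that. The scale is absolute, with 4 defined as normal function, so a Week 8 deficit is scored and counted whatever the baseline was. Clinically relevant observations are also adverse events (Section 11.2.2), although judging worsening relies on the same baseline.

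Fourth, Section 13.4 is a summary, and a detailed SAP is to follow before database lock. Section 13.4.4.7 does not order pooling of knees, and bilateral data make per-limb tables possible. So the table can still be put right in that SAP, but a baseline already measured on a numbed knee cannot.

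Finally, it is tempting to call a comparison of limbs underpowered. Section 13.4.4 plans no formal safety inference unless otherwise noted, and any power figure would rest on rates that the documents do not give.

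**Conclusion.** The point holds as a gap in timing and in the table. The protocol permits, but does not require, a baseline on a cooled or locally anesthetized knee, and no Screening or Week 4 sensory test can stand in for it. The stated summary cannot separate new deficits from pre-existing or resolved ones, or assign them to the injected limb, and at Visit 4 it mixes two different exposure states. What is lost is change and attribution, not the count of deficits at Week 8.

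The size is unknown. The illustrations rest on assumed rates, and the pooling result on one reading of a unit that the text leaves open. The conclusion itself rests only on the wording. The change is worth making because it uses data already to be collected.

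**What to change.** - **Timing.** In footnote h (for the sensory-testing row) and Sections 10.1.2, 10.1.4 and 10.3.3.2.5, state that sensory testing precedes any pre-medication, cooling or lidocaine at that visit.
- **Table.** In Section 13.4.4.7, replace the percentages per visit with descriptive per-limb shift tables from each limb's own pre-injection score, shown separately for injected and uninjected limbs. For uninjected limbs use the Visit 2 score.
- **Comparison.** Use the within-subject contrast of injected and uninjected limb mainly for type 1 subjects. Show type 3 separately, noting that the uninjected knee is a replaced joint and so a poor control.
- **Visit 4.** Label the index-knee result as a time point after the first injection, and the contralateral-knee result as that knee's baseline.

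The cost is one timing line in the protocol and a larger set of tables. No test, visit or formal hypothesis test is added.
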